1. Screening visit and baseline data collection

Study participants will come from the patient rosters of study physicians. Patients who appear to be eligible after chart review and completion of standard of care test and procedures will be invited to undergo screening for the trial. Patients considered by the clinical center investigator as likely to be eligible for participation in the trial may be consented, registered and screened at a visit that is a part of the ongoing clinical care of the patient.

An open label pilot study to be conducted at Johns Hopkins Bayview Medical Center over 9 months to evaluate with nVNS for the symptomatic exacerbations of nauseas in patients with gastroparesis or CUNV. Approximately 30 patients will be enrolled in the study. Inclusion criteria will include patients 18 years or older with symptomatic nausea, vomiting and other symptoms suggestive of chronic nausea and vomiting of presumed gastric origin (Gastroparesis or CUNV). All the participants will come from the patient roster of the study physicians from the Division of Gastroenterology, Department of medicine: [name] (Principal Investigator), and [name].

In order to minimize the need for research-only in-person visits, telemedicine visits may be substituted for in person clinical trial visits or portions of clinical trial visits where determined to be appropriate and where determined by the investigator not to increase the participants risks. Prior to initiating telemedicine for study visits the study team will explain to the participant, what a telemedicine visit entails and confirm that the study participant is in agreement and able to proceed with this method. Telemedicine acknowledgement will be obtained in accordance with the Guidance for Use of Telemedicine in Research. In the event telemedicine is not deemed feasible, the study visit will proceed as an in-person visit. Telemedicine visits will be conducted using HIPAA compliant method approved by the Health System and within licensing restrictions

Revisions to the informed consent process are being permanently adopted for this research. Teleconsent will be used as opposed to in person consenting where possible to reduce unnecessary in person encounters specifically for a consent procedure. In the event teleconsent is utilized, participants will be provided with a copy of the Informed Consent prior to the teleconsent meeting either via email, fax, mail or previously provided during an in person visit.

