As part of the screening process for the trial, the patient must have a diagnosis of gastroparesis or CUNV with delayed gastric emptying documented by gastric emptying scintigraphy (4-hour emptying after a low-fat meal with any combination of 2- and 4-hour retention of >60% and 10% respectively) and ongoing symptoms such as: nausea, vomiting, abdominal pain, etc. for at least 3 months without any other obvious cause. Patients must also have a normal upper endoscopy or standard radiography, to rule out other potential causes of symptoms such as mechanical obstruction, inflammatory or other structural lesions of the GI tract or non-gastrointestinal causes.

Recording of screening data on trial forms may not start until the patient has signed the informed consent form (ICF). Screening and baseline data collection procedures will include questionnaires, urine pregnancy test, 12 lead EKG, and review of the patient's medical chart.

All participants who sign the ICF will be registered in the trial database. Each participant who starts screening will be accounted for at the end of the screening, as either success or a screening failure. Screening failure is defined as a participant who signed the consent form and was registered in the trial data system, but is found to be ineligible prior to start of treatment. Screening failures include patients who meet medical eligibility criteria but change their mind and do not consent to participate in the trial. The reason for screening failure will be recorded and keyed into the database.

Screening visit:

The patient will undergo a medical history to identify other illness and contraindications for participations such as use of narcotics for more than 3 days per week, previous surgery of the upper gastrointestinal tract, history of prolonged QT interval or clinical significant arrhythmia, etc.

In addition, the patient will be provided with the questionnaires and will be administered on a daily basis for up two weeks before treatment with following questionnaires (delivered electronically):

- Gastroparesis Cardinal Symptom Index Daily Diary (GCSI-DD)

- Rescue medication uses daily diary- number of pills and type. Rescue medications that will be allowed for this trial are ondansetron, promethazine and prochlorperazine.
- Migraine and headache daily diary
- Gastrointestinal Symptom Rating Scale (GSRS)
- Patient Assessment of Upper Gastrointestinal Symptom Severity Index (PAGI-SYM)
- Beck Depression Inventory (BDI-II)

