 - Gastroparesis Cardinal Symptom Index Daily Diary (GCSI-DD)
 - Rescue medication uses daily diary- number of pills and type
 - Migraine and headache daily diary
 - Gastrointestinal Symptom Rating Scale (GSRS)
 - Patient Assessment of Upper Gastrointestinal Symptom Severity Index (PAGI-SYM)
 - Beck Depression Inventory (BDI-II)
 - State- Trait Anxiety Inventory (STAI)
 - Average weekly frequency of migraine for the last 4 week period
 - COMPASS-31 score.
 - Global patient impression (GCPI) questionnaire.

Laboratory test results that need to be collected are EKG and urine pregnancy test. Review study of adverse events will be addressed.

- Week 8 visit: This will be the end of study visit. A medical history, including side effect or symptom profile will be collected. The following questionnaires should be completed and collected:
 - Gastroparesis Cardinal Symptom Index Daily Diary (GCSI-DD)
 - Rescue medication uses daily diary- number of pills and type
 - Migraine and headache daily diary
 - Gastrointestinal Symptom Rating Scale (GSRS)
 - Patient Assessment of Upper Gastrointestinal Symptom Severity Index (PAGI-SYM)
 - Beck Depression Inventory (BDI-II)
 - State- Trait Anxiety Inventory (STAI)
 - COMPASS-31 score.
 - Global patient impression (GCPI) questionnaire.
- Week 10 visit: This will be the end of study visit. A medical history, including side effect or symptom profile will be collected. The following questionnaires should be completed and collected:
 - Gastroparesis Cardinal Symptom Index Daily Diary (GCSI-DD)
 - Rescue medication uses daily diary- number of pills and type
 - Migraine and headache daily diary
 - Gastrointestinal Symptom Rating Scale (GSRS)
 - Patient Assessment of Upper Gastrointestinal Symptom Severity Index (PAGI-SYM)
 - Beck Depression Inventory (BDI-II)
 - State- Trait Anxiety Inventory (STAI)
 - COMPASS-31 score.
 - Global patient impression (GCPI) questionnaire.

	Screening & GammaCore treatment Visits (Weeks)		Follow-up Visits: Weeks from start of treatment		
	Screening (0)	Treatment initiation (2)	4	8	10
Consent	X				
Baseline medical	X				
history					
GCSI-DD	X		X	X	X
Rescue Medication Daily Diary	X		X	X	X
Migraine and Headache Daily Diary	X		X	X	X
Collection of GCSI- DD		X	X	X	X
Collection of Rescue Medication Daily Diary		X	X	X	X
Collection of Migraine and Headache Daily Diary		X	X	X	X
PAGI-SYM questionnaire	X		X	X	X
GSRS questionnaire	X		X	X	X
Beck Depression Inventory-II	X		X X	X X	X X

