- Currently implanted with an electrical and/or neurostimulator device, including but not limited to cardiac pacemaker or defibrillator, vagal neurostimulator, deep brain stimulator, spinal stimulator, bone growth stimulator, or cochlear implant.
- History of carotid endarterectomy or vascular neck surgery on the right side.
- Implanted with metal cervical spine hardware or has a metallic implant near the gammaCore stimulation site.
- Any other condition, which in the opinion of the investigator would impede compliance or hinder the completion of the study.
- Failure to give informed consent.

6. **Drugs/ Substances/ Devices**

gammaCore Sapphire (nVNS) ²³⁻²⁵

Description:

nVNS is a multi-use, hand-held, rechargeable, portable device consisting of a rechargeable battery, signal-generating and -amplifying electronics, and a control button for the patient to control the signal amplitude. The device provides visible (display) and audible (beep) feedback on the device and stimulation status. A pair of stainless steel surfaces, which are the skin contact surfaces ("stimulation surfaces"), allow the delivery of a proprietary electrical signal. The patient applies electroCore-approved gel to the stimulation surfaces to maintain an uninterrupted conductive path from the stimulation surfaces to the skin on the neck. Tubes of electroCore-approved gel are provided with each unit and refill kit for this purpose. The stimulation surfaces are capped when not in use.

7. Study Statistics

Data analysis will be performed at Mayo Clinic Scottsdale, Arizona by [name], ([contact]). This site will no recruit participants.

Johns Hopkins will serve as coordinating center, responsible for overall data management, monitoring and communication among both sites, and general oversight of the conduct of this protocol.

Outcome measures

Primary: The primary outcome measure is the average daily use of rescue medications for exacerbation of nausea/vomiting.

Sample size justification

- Primary endpoint: Improvement in nausea control, as defined by a 50% reduction n the number of weekly doses of rescue medications, compared with baseline.

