- Total of 45 patients. This is a pilot study to assess the strength of the signal (improvement) with peripheral VNS for nausea. Since there is evidence that the left and right vagus may have different pathways within the CNS, with the left side being dominant in innervation of center involved in food aversion and nausea (Cell 175, 665–678, 2018), we are proposing to study three groups as follows
 - Group 1; Start with left sided stimulation 15 patients
 - Group 2. Start with right sided stimulation 15 patients
 - Group 3. Both sided stimulation 15 patients
- Our assumptions are as follows, in terms of the number of patients improving in each group

Group 1: 4/15 Group 2: 11/15 Group 3: 7/15

If these assumptions are true, the type I error will be < 0.05

8. Risks³²⁻³⁴

The adverse reactions observed in nVNS studies include:

- i. Shortness of breath (dyspnea), hoarseness, or change in voice during treatment.
- ii. Muscle twitching, discomfort, or pain during stimulation.
- iii. Change in taste (dysgeusia).

These first three reactions resolved after treatment was completed.

- iv. Local skin irritation/inflammation.
- v. Any progression of headache symptoms.

Adverse reactions not seen in the studies, but associated with implanted vagal nerve stimulation devices include:

- vi. Tingling, pricking, or a feeling of "pins and needles" on the skin where the device is applied (paresthesia or dysaesthesia) lasting beyond the treatment period.
- vii. Fainting (syncope), light-headedness, and/or dizziness.
- viii. Sweating.
- ix. Fatigue, depressed mood.
- x. Tinnitus.
- xi. Diarrhea.
- xii. Abnormal heart rhythm.

Adverse events will be evaluated in every follow-up visit. A form of Adverse Event will be completed if the candidate complains of any symptoms, sign, abnormal assessment or any combination of these. An adverse event can be expected side effect that is of a serious nature, or an unexpected side effect/event regardless of severity.

This study will monitor and report adverse events to ensure patient safety to IRB and FDA. Signs and symptoms associated with the adverse event will be graded as to severity by the clinical site staff as mild, moderate, or sever using Version 5.0 of the National Cancer Institute's Common Terminology Criteria for Adverse Events (CTCAE).

9. Benefits

Description of the probable benefits for the participant and for society.

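### The sample size replaces the named primary outcome, a daily rescue rate, with a 50% responder cut and gives no test; keeping the rate continuous and relative to baseline would raise power

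*Combined protocol and SAP*

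**What the plan says.** Section 7 (Study Statistics) gives two primary definitions. Under Outcome measures: "The primary outcome measure is the average daily use of rescue medications for exacerbation of nausea/vomiting". Under Sample size justification, the primary endpoint is "Improvement in nausea control, as defined by a 50% reduction n the number of weekly doses of rescue medications, compared with baseline".

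The same subsection sets up three groups of 15 (left first, right first, both sides) and assumes these numbers improving: "Group 1: 4/15 Group 2: 11/15 Group 3: 7/15". The only statistical statement is "If these assumptions are true, the type I error will be < 0.05". No test, model, covariate, contrast, sidedness or power is given. Nor is there an SD of the daily rate or a correlation between baseline and on-treatment rates.

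The data for a rate analysis are already planned. The screening visit in section 4 lists the "Rescue medication uses daily diary- number of pills and type", kept for up to two weeks before treatment. The visit table has a row for "Collection of Rescue Medication Daily Diary" at treatment initiation and at weeks 4, 8 and 10.

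Two other statements matter here. Section 4 says "Approximately 30 patients will be enrolled in the study", against 45 in section 7. The treatment instructions in section 4 have patients change to the other side of the neck after 4 of the 8 weeks.

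**The concern.** The only between-group comparison visible in the plan rests on one yes/no result per patient, although weeks of daily counts are collected. With 15 per group, that loss of information is expensive.

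The comparison also has no named target. Three groups can differ overall without showing which side to take forward, and the assumed counts put Group 3 between the other two. Someone relying on section 7 would not see that the comparison has about a one-in-three chance of missing its own assumed effect, or that Group 3 is unlikely to be separated from either arm.

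**Working it through.** **1. The plan's own figure.** Inputs are the assumed counts 4, 11 and 7 of 15 (section 7). The pooled proportion is 22/45 = 0.489 and the mean count is 7.333.

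X² = [(4 − 7.333)² + (11 − 7.333)² + (7 − 7.333)²] / (15 × 0.489 × 0.511) = 24.667 / 3.748 = 6.58 on 2 df, p = 0.037.

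This agrees with the plan's statement that the figure is below 0.05. It is the p-value of the assumed table, however, not a type I error and not a power.

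**2. Pairwise results if those counts occur exactly (two-sided Fisher).**

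| Pair | p |
|---|---|
| Left 4 v right 11 | 0.027 |
| Left 4 v both 7 | 0.45 |
| Right 11 v both 7 | 0.26 |

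The first is not below 0.05/3 = 0.0167 if all three pairs are tested. Group 3 differs from neither arm.

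**3. Power on responder counts.** This is the sum of the binomial probabilities of all tables that reach significance at 0.05, at the assumed rates and 15 per group.

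| Comparison | Test | Power |
|---|---|---|
| Three groups | Chi-square | 65.6% |
| Left v right | Fisher | 59.6% |
| Left v right | Chi-square | 74.4% |

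**4. Same effects without the cut, by normal theory.** Assume the change from baseline on the log scale is normal. The rates 4/15, 11/15 and 7/15 then correspond to shifts of −0.623, +0.623 and −0.084 SD, with mean −0.028.

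λ = 15 × (0.595² + 0.651² + 0.056²) = 11.71.

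The non-central F with 2 and 42 df gives 84.9%, with no covariate. Left v right by t-test gives 91%. A logistic shape gives 76% for three groups.

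**5. Diary simulation.** All inputs beyond the responder rates are assumptions: 14-day baseline, 28-day window, Poisson counts, median 1 dose per day, between-patient log-SD 0.6, and SD of the log ratio 0.5, 0.7 or 0.9. Group effects are calibrated to the plan's responder rates. Three-group power over repeated runs at 15 per group:

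| Analysis | Power |
|---|---|
| Responder counts, chi-square | 62% to 69% |
| Log change from baseline, no covariate | 79% to 84% |
| ANCOVA, log rate on log baseline rate | 80% to 85% |
| On-treatment log rate alone | 58% to 76% |

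Left v right by ANCOVA is about 87% to 92%. Type I error of the ANCOVA tests is about 4% to 5.5%.

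Varying the SD tests little, because the effects are recalibrated to the same responder rates each time.

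**6. Varying the correlation r between true log baseline and log on-treatment rates.** Assumptions: 2 doses per day, log-SD 0.6, 14-day baseline, 56-day window.

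| r | Responder counts | Log change | ANCOVA |
|---|---|---|---|
| 0.3 | 61% | 78% | 95% |
| 0.5 | 59% | 76% | 90% |
| 0.7 | 56% | 72% | 84% |
| 0.9 | 41% | 53% | 60% |

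Normal theory with a baseline covariate gives 96% (r = 0.3) to 87% (r = 0.9). The overall range is therefore about 60% to 96%, and ANCOVA is above the responder count in every diary simulation.

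**7. About 30 patients.** With 10 per group and the settings of step 5, responder counts give about 42% to 45% (43.3% by enumeration) and ANCOVA 59% to 63%.

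**The case against.** The strongest reply is that the plan has not chosen a poor analysis, because it states none. The named primary outcome measure is already the daily rate, and the responder count appears only under sample size. That stands: the defect is two conflicting primary definitions with no method. The endpoint attached to the sample size is nevertheless the dichotomised one, so a statistician following section 7 could reasonably analyse it.

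A reader might infer that adding a baseline covariate is what lifts power from about 65% to 84%. The calculation does not support this. Step 4 reaches 84.9% with no covariate, and in step 5 the log change score does as well as ANCOVA. In step 6, where change depends on baseline, the covariate adds about 6 to 16 points, but dropping the cut still accounts for at least half of the gain. Nor is the planned comparison blind to baseline, since the responder definition is relative to it.

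The left v right gain also depends on the comparator. Against Fisher it is about 30 points, but against chi-square (74%) it is roughly half that.

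It is also tempting to argue from chance baseline imbalance under randomisation. The documents describe no random allocation to the three groups, so that argument is not used here.

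Finally, this is a pilot whose principal objective is whether rescue use falls. That limits the weight of the point but does not remove it, because section 7 rests the sample size on the group comparison.

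**Conclusion.** The concern holds in a limited form. Section 7 names a daily rate as primary, sizes the trial on a 50% cut of that rate, and specifies no analysis. On the plan's own assumed counts, three-group power is 65.6%, and Group 3 separates from neither arm even if the counts occur exactly. These figures need nothing beyond the protocol and a choice of test.

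The gain to roughly 80% to 85% rests on assumed Poisson counts, lognormal patient variation and 15 per group. It should not be quoted as a property of this trial, because the documents give neither an SD nor a correlation and the wider range is about 60% to 96%. The direction was the same in every diary simulation.

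Use of baseline in some form matters. In step 5, ANCOVA and the log change score clearly beat the on-treatment rate alone, although that margin shrinks if the correlation is low. If enrolment is about 30, power is low either way and the loss from the cut is of similar size.

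**What to change.** Before data are examined:

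- Make the daily rescue rate the analysed primary endpoint, so that the two statements in section 7 agree.
- Compare groups with a negative binomial model with a log-days offset, or ANCOVA on the log scale, with log baseline daily rate and group as terms. The negative binomial model handles patients with no on-treatment doses; ANCOVA needs a stated zero rule. Either needs a rule for a baseline of zero. The power figures above are for the log-scale analyses; the negative binomial model was not simulated.
- Use the first 4 weeks, before the change of side, for the side comparison. An 8-week average would mix sides.
- Name left-first v right-first as the single between-group contrast. Report Group 3 by estimate and confidence interval only.
- Keep the 50% responder share as a descriptive secondary.
- Replace the type I error sentence with a power statement that names its test and assumptions, and reconcile 30 with 45 patients.

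The cost is about one paragraph of text and slightly more analysis work, with no new data. The downside is that the headline becomes a rate ratio, which is less immediate to clinicians than a responder percentage.

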- State- Trait Anxiety Inventory (STAI)
- Average weekly frequency of migraine headaches for the last 4 week period
- COMPASS-31 score.

Anthropomorphic assessments (body weight, body height, body mass index [BMI]. Pregnancy test results that need to be recorded from chart review or obtained as part of the screening and EKG to rule out any abnormal baseline electrocardiogram such as second and third degree heart block, atrial fibrillation, atrial flutter, recent history of ventricular tachycardia or ventricular fibrillation, or clinically significant premature ventricular contraction, history of prolonged QT interval or a history of clinically significant arrhythmia.

Data will be captured on REDCAP and stored on the secure Hopkins server for this purpose.

2. Treatment Start Visit

At this visit, the patient will receive the gammaCore (nVNS) device and a video instruction will be use to explain how to properly handle the device. Treatment can only start after eligibility has been fully checked and all data collected at screening have been keyed into the trial database. Women of childbearing potential must have a negative urine pregnancy test.

After eligibility is confirmed with the clinical center staff the treatment can begin. The date of starting treatment is the start (ZERO) time for the timing of follow-up visits.

Frequency and duration of nVNS treatment.

The treatment will be self-administered using nVNS and will be applied for 8 weeks; 4 weeks will be used on one side of the neck and other 4 weeks in the contralateral side. A member of the study will provide the proper training on the correct use of nVNS. The patient will be instructed to use the nVNS in place of the rescue medications. When the nauseas gets bad enough that they feel to use a rescue medication they will first use the device on one side of the neck for two 2minute stimulations and wait fifteen minutes to check if the stimulation works. If this does not help either, they will stimulate with an additional 2 stimulations and wait for another fifteen minutes. If there is no improvement rescue medication will be used. nVNS can be used up to, but no more than, 8 times a day.

3. Follow-up Visits

Patients will return for follow-up visits at 4 and 10 weeks after treatment initiation. The specific

procedures to be completed at each of the follow-up visits are:

- Week 4 visit: The following questionnaires should be completed and collected:

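### Section 7 justifies 45 patients by comparing three side-of-stimulation groups, but no method of assigning patients to groups is described, so that comparison is open to selection bias

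*Combined protocol and SAP*

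**What the plan says.** Section 7 (Study Statistics, sample size justification) sets a total of 45 patients and says "we are proposing to study three groups as follows". It defines the groups as "Start with left sided stimulation 15 patients", "Start with right sided stimulation 15 patients" and "Both sided stimulation 15 patients". It then gives the assumed numbers improving, "Group 1: 4/15 Group 2: 11/15 Group 3: 7/15", and concludes "If these assumptions are true, the type I error will be < 0.05". No test, power or rule for multiple comparisons is named.

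The same section describes the purpose in softer terms: "This is a pilot study to assess the strength of the signal (improvement) with peripheral VNS for nausea". The responder definition is a halving of weekly rescue doses relative to the patient's own baseline.

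Section 4 (Frequency and duration of nVNS treatment) does not mention the three groups. It gives one regimen for everyone: "4 weeks will be used on one side of the neck and other 4 weeks in the contralateral side". It does not say how the first side is chosen.

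On how a patient would reach a group:
- The treatment start visit in Section 4 lets treatment begin once eligibility is confirmed, with no assignment step.
- The visit schedule has no row for allocation.
- The recruitment text has patients approached by their own physicians, who belong to the study team.
- Sections 2 and 4 call the study open label.

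**The concern.** The only quantitative argument for the sample size is a comparison between groups, and nothing says how the groups are formed. As written, a list, alternation, filling the groups in sequence, or a choice by physician or patient would all comply with the protocol.

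The setting makes this matter. Staff and patients know the side. The assumed counts show a strong prior expectation about side (4/15 against 11/15). The population mixes gastroparesis and chronic unexplained nausea and vomiting, with varying as-needed antiemetic use, and response is measured against each patient's own baseline. If diagnosis, severity or calendar time differs between groups, a left/right/both difference could arise with no effect of side. No baseline adjustment is planned, and poor allocation cannot be repaired after enrolment.

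**Working it through.** **1. What the type I error sentence is.** Inputs from Section 7: 15 per group; responders 4, 11 and 7; total 22 of 45.

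- Expected responders per group: 15 × 22/45 = 7.333.
- Sum of squared deviations: (4 − 7.333)² + (11 − 7.333)² + (7 − 7.333)² = 11.111 + 13.444 + 0.111 = 24.667.
- Variance term: 15 × (22/45) × (23/45) = 3.748.
- Pearson chi-square = 24.667 / 3.748 = 6.58 on 2 degrees of freedom, p = 0.037.

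The likelihood-ratio test gives p = 0.033 and the exact test p = 0.046. The stated figure is therefore reproduced as a p-value at the assumed counts. It is not an error rate. It does confirm that the case for 45 patients is a between-group comparison.

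**2. Search for an allocation rule.** I read the objectives, the screening, treatment start and follow-up visits, the visit schedule, recruitment, eligibility and statistics. None mentions randomisation, a sequence, concealment, stratification, alternation or any other rule. The opening part of the document was not available for this check, but every section where allocation would normally stand was present.

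**3. Size of the possible bias (illustration).** The documents give no figures for this, so the following are assumptions: no true side effect; good-prognosis patients respond 65% of the time and others 35%; the share of good-prognosis patients is 30% in left first, 70% in right first and 50% in both sides.

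- Left first: 0.30 × 65% + 0.70 × 35% = 44%.
- Right first: 0.70 × 65% + 0.30 × 35% = 56%.
- Both sides: 0.50 × 65% + 0.50 × 35% = 50%.
- Spurious left–right difference: 56 − 44 = 12 points. Section 7 assumes (11 − 4)/15 = 47 points.

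Full enumeration of three binomials of 15, with nominal 5% chi-square critical values of 5.991 (2 df) and 3.841 (1 df), gives these rejection rates at 44/56/50%:
- three-group test: 8.4%, against 5.0% when all rates are equal;
- left versus right: 9.3%.

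**4. Range.** With a wider prognostic gap (70% against 30%), the three-group false-positive rate is:

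| Good-prognosis share, left/right/both | False-positive rate |
|---|---|
| 50/50/50% | 5.0% |
| 40/60/50% | 6.5% |
| 30/70/50% | 11.2% |
| 20/80/50% | 19.9% |
| 10/90/50% | 33.2% |

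The last rows need extreme imbalance and show direction only.

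**The case against.** The strongest reply is that this is a pilot with a before–after objective. Section 2 asks whether nVNS reduces rescue medication use, the primary outcome is average daily rescue use, and the responder endpoint is relative to baseline. None of that needs randomised groups, and no between-group test is formally specified. This stands, and it limits the point to the side comparison. It does not remove the point, because that comparison is the only support offered for 45 patients.

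Second, a reader might infer that allocation is non-random, or that physicians or patients choose the side. The documents do not support that. They are silent on the method, and randomisation may be intended. What can be said is that no random allocation is described and that the protocol as written would permit selection.

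Third, if the side-switching in Section 4 also applies to the left-first and right-first groups, each of those patients supplies data on both sides. A within-patient contrast would not be confounded by diagnosis or severity, although period effects would remain. This is fair, but the plan does not specify that analysis, and Section 7 counts responders by group.

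Fourth, the bias figures rest on invented prognosis splits, and at the main setting the inflation is modest. That also stands; the figures illustrate a mechanism and do not predict what this trial would show.

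**Conclusion.** The point holds for the side comparison. Section 7 relies on a three-group comparison, and the protocol describes no way of forming the groups. On the assumed 30/70/50% split with 65% and 35% response, the false-positive rate is about 8% (three groups) or 9% (left versus right) instead of 5%. It is less with milder imbalance and more with stronger imbalance or a wider prognostic gap. The actual size cannot be known from the documents.

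Two stronger readings should be avoided. The first is that the trial's main result is compromised: change in rescue medication use from baseline does not depend on how side is allocated. The second is that randomising would make the type I error sentence correct: 0.037 is a p-value conditional on the assumed counts, the arithmetic is the same under any allocation, and the sentence is mislabelled either way.

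**What to change.** 1. First reconcile Section 4, which gives a single regimen with a change of side and no both-sided group, with the three groups in Section 7. The approximately 30 patients in Section 4 and the 45 in Section 7 need reconciling at the same time.
2. Then state in Sections 4 and 7 that patients are randomised 1:1:1 by a concealed, computer-generated list, for example in the REDCap system already used for data capture. Assignment should be released after eligibility is confirmed and before the device is dispensed. Add this step to the visit schedule, and analyse patients by allocated group.
3. If allocation will not be random, label the group comparison descriptive and justify the number of patients on change from baseline.
4. In either case, replace the type I error sentence. Name the test, give the significance level as a design choice, and state the power. For reference, with 15 per group and the assumed rates, the three-group chi-square test at two-sided 0.05 has 65.6% power.

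The allocation itself costs one list and a few sentences, with no added patients or visits. Reconciling the regimen with the groups is the larger task, but it is needed whatever is decided about randomisation. All of this must be settled before enrolment.
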